### **23.1.2 Primary Objective**

The primary objective of the TRTT is to assess the efficacy of TRT, defined as DC and ST achieved through conventional SGs (Group 1) as a treatment for severe debilitating tinnitus. The primary outcome to be measured in the TRTT is the difference in scores on the Tinnitus Questionnaire (TQ) between baseline and follow-up assessed longitudinally, at 3, 6, 12, and 18 months of treatment. The corresponding hypothesis is that TRT (Group 1 in Table 22.1) compared with the standard of care (SC; Group 3) will reduce the severity of debilitating tinnitus significantly as assessed by longitudinal changes in the TQ score and at the end of treatment..

The secondary efficacy outcomes will test the following hypotheses. TRT (Group 1) compared with SC (Group 3) will reduce severity of debilitating tinnitus significantly as assessed by longitudinal changes in:

Score on the following tinnitus and functional measures:

- Sub-scales of the TQ;
- Tinnitus Handicap Inventory;
- Tinnitus Functional Index;
- TRT Visual Analogue Scale; and
- Digit Symbol Substitution Task.

and psychoacoustic measures:

- Tinnitus Pitch and Loudness Match; and
- Loudness Discomfort Level (LDL)

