### 23.3.2.1 Primary Outcome

The primary outcome variable will be change in the TQ score. We will use spaghetti plots for initial exploratory analyses and longitudinal data analyses as our primary analytic method. Longitudinal analyses allows us to account for the natural correlation which occurs with observations on the same subject over time and for the same Audiologist observing several Study Participants. Indicator variables will identify group; their coefficients in the models represent the primary focus on group differences. Adjustment for covariates such as age and sex can easily be accounted for in this class of models.

Mean TQ scores will be compared between two treatment groups using Generalized Estimating Equations (GEE) as implemented in STATA, SAS or R. The basic model is as follows:

Let  $TQ$  denote the TQ score. We expect effects of Clinical Center, Audiologist, treatment group, and possibly personality traits as measured by the State-Trait Anxiety Index (STAI) or Positive and Negative Affect Schedule (PANAS); or other factors such as hearing difficulty measured using the Hearing Handicap Inventory (HHI), or early completion of treatment. We will use models of the form:

$$TQ_{ijkgt} = \beta_0 + \beta_c C_j + \beta_a A_k + \gamma_g G_g + \tau T_t + \rho_1 PT_{1i} + \rho_2 PT_{2i} + \varepsilon_{ijkgt}$$

where:

j indexes Clinical Center;  
k indexes Audiologist;  
g indexes Group;  
t indexes Time; and  
I indexes Study Participant.

Both Study Audiologist and Study Participant are nested within Clinical Centers. The parameter of interest is  $\gamma_g$ , with  $\gamma_1$  representing the difference between Group 1 (full TRT) and Group 3 (SC). (G represents a dummy variable for Groups).  $\beta_a$  and  $\beta_c$  provide comparisons between Study Audiologists and Clinical Centers; C and A are dummy variables.  $\tau$  captures the effect of time;  $T_1$  has the values of 0, 3, 6, 12, and 18.  $\rho_1$  and  $\rho_2$  capture differences in psychometric instruments measurements, e.g., the STAI and PANAS, respectively. Other factors may also be included as necessary ( $\rho_3$ ,  $\rho_4$ , etc.).

Similar models will be run for the secondary objectives. The mean TQ scores will be compared between the Group 1 (DC + conventional SG) and Group 2 (DC + placebo SG) for the superiority of the conventional SG; and between Group 2 (DC + placebo SG) and Group 3 (SC)

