### **23.3.2.2 Secondary Efficacy Analyses**

For the analyses looking at the difference between TQ score at baseline and 18 months, we will compare TQ mean scores at 18-month in the treatment phase among treatment groups using Analysis of Covariance (ANCOVA). We will adjust for Baseline TQ scores and heterogeneity of

tinnitus status in the patient population. We will also adjust for important baseline covariates and variables that may be unbalanced at baseline (even with randomization) and are potentially related to TQ score. We will also use GEE for this analysis.

The data resulting from this project will enable us to address a number of additional research questions. First, to assess the effect of the interventions on different aspects of tinnitus morbidity, we will use the approach described above with other outcome variables, including the TQ subscales, global and subscale scores of the Tinnitus Functional Index, the Tinnitus Handicap Inventory, and the visual analog scale of the TRT Interview instrument. We will also compare baseline audiometric measures, and psychoacoustic variables of Tinnitus Loudness Match and Loudness Discomfort Level to evaluate whether there is any change across time in these measures.

The secondary outcome variables are the same for both the primary objective and the secondary objectives. For both the objectives, all of the longitudinally assessed variables (for example, subscales of TQ, Tinnitus Handicap Inventory, Tinnitus Functional Index, TRT-Visual Analog Scale, Digit Symbol Substitution Task, tinnitus pitch and loudness match, and LDL) will be treated as the TQ score (primary efficacy outcome analysis) using GEE. The respective mean scores will be compared between corresponding treatment groups (as described in the previous section) over the entire treatment phase. Both the differences in mean responses between treatment groups and the rate of change over time will be of interest in these analyses.

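### The primary GEE equation treats baseline TQ as one of five outcome visits and tests only a group main effect, so its parameter of interest is diluted toward no effect and is not the declared primary outcome

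*Combined protocol and SAP*

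**What the plan says.** Section 23.1.2 defines the primary outcome as "the difference in scores on the Tinnitus Questionnaire (TQ) between baseline and follow-up assessed longitudinally, at 3, 6, 12, and 18 months of treatment". Section 23.3.2.1 opens the same way: "The primary outcome variable will be change in the TQ score". The assumptions in 23.2.3 count four follow-up time points, without month 0.

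The equation in 23.3.2.1 is different. Its response symbol is defined to "denote the TQ score. We expect effects of Clinical Center, Audiologist, treatment group" and other factors, so the left-hand side is the score and not its change. Time "has the values of 0, 3, 6, 12, and 18", so the baseline visit enters as an outcome row. The right-hand side has Clinical Center, Audiologist, group, one time term and personality measures. It has no group-by-time term and no baseline TQ. The parameter of interest is γ, with γ₁ the Group 1 versus Group 3 difference. Of the group indicators the text says "their coefficients in the models represent the primary focus on group differences".

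The same section applies similar models to the two component comparisons. Section 23.3.2.2 applies the approach to all longitudinal secondary outcomes, adding: "Both the differences in mean responses between treatment groups and the rate of change over time will be of interest in these analyses". For the separate 18-month ANCOVA, 23.3.2.2 states: "We will adjust for Baseline TQ scores". The primary equation has no such adjustment. Section 23.3.2.1 describes GEE as flexible about covariance but names no working correlation.

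**The concern.** Nobody has been treated at month 0, and assignment is randomized, so the expected group difference there is zero whatever the treatment does. A group main effect fitted across months 0 to 18 forces one common difference on all five visits, and so mixes that zero with the four differences the trial was built to measure. The estimate and its confidence interval are then centred too close to no effect.

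The model also leaves out baseline TQ as a covariate, so stable between-person differences in TQ stay in the error of the group contrast. The sample size rests on the SD of change scores, from which those differences have been removed. The stated power is therefore not the power of the equation as written. The same form carries through to both component comparisons and to the longitudinal secondary outcomes, where no term captures a group difference in rate of change.

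**Working it through.** **The plan's own figure.** Inputs from 23.2.2 and 23.2.3: difference 7, change SD 12.5, two-sided alpha 0.05/3, power 80%, attrition 10%. The normal formula gives 67 per group; 67/0.9 rounds up to 75, or 225 in total. The t-based version gives 69 per group; 69 × 1.1 = 75.9, or about 228 in total. The stated 228 (76 per group) is reproduced. With 68 completers per group (76 × 0.9), power is 81% for 7 points and 99% for 10.

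**What γ estimates.** With complete, balanced data and working covariance V, the group coefficient is γ̂ = w′D. D holds the five visit-specific group differences and w = V⁻¹1 / (1′V⁻¹1). The expected first element of D is 0.

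- Independence or exchangeable: every weight is 1/5, so γ is 4/5 of the mean follow-up effect for any effect profile. A constant 10 gives (0 + 10 + 10 + 10 + 10)/5 = 8; a constant 7 gives 5.6.
- Independence with 10% missing at each follow-up visit and a constant effect: month-0 weight 1/(1 + 4 × 0.9) = 0.217, dilution 21.7%.
- AR(1) by visit, correlation 0.3 to 0.9: 24% to 44% for a constant effect, 10% to 18% for an effect rising linearly to month 18.
- Correlation decaying with months: 20.5% to 40% constant, 8% to 12% rising.
- Unstructured covariance: 36% if baseline is less correlated with follow-up (0.5) than follow-up visits are with each other (0.7). It is 65% if baseline also has 0.8 times the follow-up SD (correlations 0.6 and 0.7), and 3% to 7% if baseline SD is 1.2 times the follow-up SD.
- Change score at the four follow-up visits only: no dilution.

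The correlations, SD ratios and effect profiles are assumptions; the documents give none of them.

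**Simulation check.** GEE fits to 200 simulated trials (76 per group, SD 12.5, correlation 0.5, constant effect −10) gave a mean γ of −7.9 (Monte Carlo SE 0.11) under both independence and exchangeable. Dropping month 0 gave −9.85 with baseline adjustment and −9.83 with change scores.

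**Against the month-18 effect.** If the effect rises linearly to 10 at month 18, then under independence or exchangeable correlation γ = 10 × [(0 + 3 + 6 + 12 + 18)/5]/18 = 4.3. The mean over the four follow-up visits alone would be 10 × (39/4)/18 = 5.4. So most of the gap to 10 comes from averaging over visits, and the step from 5.4 to 4.3 is the month-0 dilution. If instead the effect wanes from month 3 to half its size at month 18, γ lies 24% above the month-18 effect.

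**Power.** Assume equal variances and a common visit correlation ρ, a change SD of 12.5, 68 per arm, alpha 0.05/3 and a constant effect. Then σ² = 12.5²/[2(1 − ρ)].

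- As written: the variance of a person's five-visit mean is σ²(1 + 4ρ)/5 and the expected contrast is 0.8 times the effect. At ρ = 0.5: σ² = 156.25, variance 93.75, SD 9.68, SE = 9.68 × √(2/68) = 1.66, and 5.6/1.66 = 3.37, giving power of about 83%. At ρ = 0.6 and 0.7 it is 66% and 46%. For 10 points: 99%, 95% and 81%.
- Follow-up visits adjusted for baseline: variance σ²[(1 + 3ρ)/4 − ρ²]. At ρ = 0.5 this is 58.6 (SE 1.31, 7/1.31 = 5.3). At ρ = 0.7 it is 74.2 (SE 1.48, 7/1.48 = 4.7). Power for 7 points is about 99% or more throughout.

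These figures ignore any variance explained by Clinical Center, Audiologist or the personality measures.

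**The case against.** The plan repeatedly calls the outcome change in TQ, and the equation is introduced as a basic form to which other factors may be added. On that view the fault is an inconsistency, and an analyst following 23.1.2 would analyse change at four visits with no dilution. The inconsistency stands, and a reader should not infer that a diluted estimate is certain to be reported. But this equation is the only primary model written in the chapters available here (the document is the second of two parts). Relabelling the response as change does not rescue it, because change at month 0 is zero for everyone. Nor does adding baseline TQ while month 0 stays an outcome row: the adjustment has expectation zero, so the factor of 0.8 remains.

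The 18-month ANCOVA adjusts for baseline, and 23.1.2 also ties the primary hypothesis to the end of treatment. An undiluted 18-month contrast is therefore planned. It sits under secondary efficacy analyses, however, and does not repair the longitudinal primary estimate.

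On power, 23.2.1 equates effect sizes of 0.8 to 1.0 with 10 to 13 points, an SD of about 12.5 to 13. If that is the raw-score SD, which the text does not say, then ρ = 1 − 12.5²/(2 × SD²), or 0.50 to 0.54. Power for 7 points is then 83% to 77%, near the stated 80%, and 98% to 99% for 10. This stands: the low figures come from the end of the range with less support in the documents.

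Finally, the sentence on rate of change concerns the secondary outcomes and does not explicitly promise a between-group comparison of rates.

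**Conclusion.** The equation in 23.3.2.1 is wrong as written. Its parameter of interest does not estimate the primary outcome in 23.1.2 and is biased toward no effect. The dilution relative to the mean follow-up effect is exactly 20% with complete data and an independence or exchangeable working correlation.

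A reader might infer that 20% is a minimum. The documents do not support that: the working correlation is unspecified, and plausible choices give anything from about 3% to 65%. A reader might also infer that the trial is underpowered. That depends on a visit correlation the documents do not give. At 0.5 the stated 80% for the component comparisons is roughly met, and the primary comparison keeps 95% or more up to about 0.6. What does fail is the description of the sample size in 23.2.3 as conservative because the analysis is longitudinal: for 7 points it does not hold for this equation at correlations of 0.6 or 0.7. There is no added risk of a false positive, since the group difference is zero at every visit under the null.

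**What to change.** Reconcile 23.1.2, 23.2.3 and 23.3.2.1 by replacing the equation with a model for TQ at months 3, 6, 12 and 18 only, with baseline TQ, Clinical Center, visit, group and group-by-visit. An equivalent is to keep month 0 as a response and constrain the group means to be equal there.

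Define the primary contrast as the Group 1 minus Group 3 difference averaged over the four follow-up visits, with the month-18 contrast read from the same model. Name the working correlation. Use the same form for Group 1 versus Group 2, Group 2 versus Group 3 and the longitudinal secondary outcomes; the group-by-visit terms then also show whether the groups diverge over time. State the power in 23.2.3 for this contrast, with the assumed visit correlation.

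The cost is SAP wording and programming. No new data, visits or participants are needed.

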### **23.3.2.2 Secondary Efficacy Analyses**

For the analyses looking at the difference between TQ score at baseline and 18 months, we will compare TQ mean scores at 18-month in the treatment phase among treatment groups using Analysis of Covariance (ANCOVA). We will adjust for Baseline TQ scores and heterogeneity of

tinnitus status in the patient population. We will also adjust for important baseline covariates and variables that may be unbalanced at baseline (even with randomization) and are potentially related to TQ score. We will also use GEE for this analysis.

The data resulting from this project will enable us to address a number of additional research questions. First, to assess the effect of the interventions on different aspects of tinnitus morbidity, we will use the approach described above with other outcome variables, including the TQ subscales, global and subscale scores of the Tinnitus Functional Index, the Tinnitus Handicap Inventory, and the visual analog scale of the TRT Interview instrument. We will also compare baseline audiometric measures, and psychoacoustic variables of Tinnitus Loudness Match and Loudness Discomfort Level to evaluate whether there is any change across time in these measures.

The secondary outcome variables are the same for both the primary objective and the secondary objectives. For both the objectives, all of the longitudinally assessed variables (for example, subscales of TQ, Tinnitus Handicap Inventory, Tinnitus Functional Index, TRT-Visual Analog Scale, Digit Symbol Substitution Task, tinnitus pitch and loudness match, and LDL) will be treated as the TQ score (primary efficacy outcome analysis) using GEE. The respective mean scores will be compared between corresponding treatment groups (as described in the previous section) over the entire treatment phase. Both the differences in mean responses between treatment groups and the rate of change over time will be of interest in these analyses.

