**Table 23.1 Schematic showing the three study groups**

	Sound therapy	“Counseling”
Group 1 (TRT)	Conventional Sound Generator	DC
Group 2 (partial TRT)	Placebo Sound Generator	DC
Group 3 (Standard of care)	Recommendation to use ambient sound	Standard clinical consultation as provided in the military

Randomization helps to ensure that treatment groups are balanced with respect to pretreatment characteristics, although analyses of departures from balance will be carried out with appropriate adjustment to treatment effect estimation, if needed. Randomization will be performed using permuted blocks of random size, and stratified by Clinical Center. The logistics of the randomization are described in Chapter 5, Patient Entry into the Study.

An important feature of this study is that every effort is made to keep the Study Audiologists and Study Participants blinded with respect to the type of sound generator (SG), either conventional or placebo.

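### The 18-month ANCOVA does not pre-specify Clinical Center, the only stratification factor named; if it is left out and center is prognostic, a little precision is lost

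*Combined protocol and SAP*

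**What the plan says.** Section 23.1.1 describes the allocation: "Randomization will be performed using permuted blocks of random size, and stratified by Clinical Center". No other stratification factor is named there.

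Section 23.3.2.1, on the primary outcome, says "We expect effects of Clinical Center, Audiologist, treatment group" and writes the GEE model with indicator variables for center and audiologist.

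Section 23.3.2.2 covers the 18-month comparison: "we will compare TQ mean scores at 18-month in the treatment phase among treatment groups using Analysis of Covariance (ANCOVA". It then gives the adjustment in two parts. The named part is "We will adjust for Baseline TQ scores and heterogeneity of" tinnitus status. The open part is "We will also adjust for important baseline covariates and variables that may be unbalanced at baseline (even with randomization", limited to those that may bear on TQ. The paragraph ends: "We will also use GEE for this analysis". It does not list that GEE's covariates or say which of the two methods is the reference.

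The end-of-treatment comparison also appears in the primary hypothesis for Group 1 versus Group 3 in Section 23.1.2: "as assessed by longitudinal changes in the TQ score and at the end of treatment".

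**The concern.** The plan treats center as prognostic in one model and does not name it in the next. The rule for adding unbalanced variables is unlikely to bring it in, because blocked allocation within center keeps the arms close to balanced on center by design.

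Center-stratified allocation removes between-center variation from the treatment difference. An ANCOVA without center still counts that variation as residual noise. If center predicts 18-month TQ beyond the other covariates, the reported standard error then exceeds the true one, intervals are too wide and tests are conservative. What is at stake is some precision in the 18-month comparison, and a decision about the stratification factor that is left open when it could be settled in advance.

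**Working it through.** **Inputs from the documents.** Section 23.2.3: SD 12.5, differences of 7 and 10 points, two-sided alpha 0.05 divided among three comparisons, 80% power, 10% attrition, 76 per arm (228 in total). Section 21.3: six centers.

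**Assumptions, not in the documents.** Alpha is split equally, 0.05/3 = 0.0167, so z = 2.394. A share ρ of the residual 18-month variance lies between centers. The SD of 12.5 is taken as the total residual SD. It is an SD of change scores, so the residual SD after baseline adjustment should be no larger. The percentage excess in the standard error depends only on ρ, not on the SD.

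**1. The plan's own figure.** n per arm = 2 × 12.5² × (2.394 + 0.842)² / 7² ≈ 66.8, so 67. Then 67/0.9 = 74.4, so 75 per arm and 225 in total, against 228 stated. A noncentral-t calculation gives 69 per arm and 230 to 231 in total. Undivided alpha gives 171, so the split is needed to reproduce the plan. With 76 × 0.9 ≈ 68 evaluable per arm, normal-approximation power is 80.8% for 7 points and 98.8% for 10, in line with the stated 80% and more than 95%.

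**2. Standard errors.** Without center: SE = 12.5 × √(2/68) = 2.144. With center: SE × √(1−ρ). The excess is 1/√(1−ρ) − 1.

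**3. Power and error rate.** For a difference δ:
- with center: Φ(δ / [SE√(1−ρ)] − z)
- without center: Φ((δ − z·SE) / [SE√(1−ρ)])
- true two-sided error without center: 2[1 − Φ(z/√(1−ρ))]

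Example with ρ = 0.05 and δ = 7: SE with center = 2.089. With center, 7/2.089 − 2.394 = 0.956, so about 83.1%. Without center, (7 − 5.132)/2.089 = 0.894, so 81.4%.

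| ρ (assumed) | SE with center | SE without center too wide by | Power, 7 points: without → with | Power, 10 points: without → with | True error without center (nominal 1.67%) |
|---|---|---|---|---|---|
| 0 | 2.144 | 0% | 80.8 → 80.8% | 98.8 → 98.8% | 1.67% |
| 0.02 | 2.122 | 1.0% | 81.1 → 81.7% | 98.9 → 99.0% | 1.56% |
| 0.05 | 2.089 | 2.6% | 81.4 → 83.1% | 99.0 → 99.2% | 1.40% |
| 0.10 | 2.034 | 5.4% | 82.1 → 85.3% | 99.2 → 99.4% | 1.16% |

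The power column without center rises with ρ because the total SD is held at 12.5 and stratification reduces the true variability of the estimate. At an extreme ρ of 0.20, power for 7 points is 83.5% without and 89.6% with center.

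**4. Simulation check.** 10,000 trials per setting, six centers of 34, 1:1:1 allocation in blocks of 3 and 6 within center (block and center sizes assumed).
- ρ = 0.10: mean model SE without center 2.14, against an actual SD of the estimate of 2.03 to 2.06. Type I error was 1.16% without and 1.60% with center. Power for 7 points was 81.2% and 84.7%.
- ρ = 0.05: power 80.7% and 82.4%. Type I error was 1.64% and 1.95%. The Monte Carlo standard error is √(0.0167 × 0.9833/10,000) ≈ 0.13 points, so 1.95% is a high draw. The test with center is exact under this model.
- ρ = 0.02: power 80.3% and 80.8%.

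**5. Degrees of freedom.** Six centers need five dummies. With 3 × 68 = 204 evaluable participants, three arms and baseline TQ, the residual degrees of freedom go from 200 to 195.

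**The case against.** The strongest reply is that the text does not leave center out. The covariate list is open, and center is known at randomization and expected to affect TQ, so it could fairly be counted among the important covariates. This stands: the gap is in pre-specification. A reader might infer that the ANCOVA excludes center, but the documents do not say so.

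Second, a GEE is planned for the same comparison, and the model in Section 23.3.2.1 carries center. This answers the concern only in part. Section 23.3.2.2 does not give the 18-month GEE's covariates. The model in Section 23.3.2.1 has a group term and a time term but no group-by-time term, so as written it yields a difference averaged over visits, not one specific to 18 months.

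Third, a reader might infer from Section 23.1.2 that the primary hypothesis is weakened. The end-of-treatment wording there concerns Group 1 versus Group 3, which is planned for 10 points, and the loss on that contrast is negligible. The larger losses fall on the 7-point contrasts. These are secondary objectives, and Section 23.1.3 states their total-TQ hypotheses longitudinally. Section 23.3.2.1 makes the longitudinal model the main analysis, and it includes center.

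Fourth, the sample size used the full SD of 12.5 with no credit for center, so the trial loses nothing that it was promised. This stands as well.

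**Conclusion.** The point holds as a minor, essentially free improvement. Center is the only stratification factor named, the plan expects it to matter, and its place in the 18-month ANCOVA is not assured. If it is omitted, and if center explains 2% to 10% of the residual variance, standard errors are about 1% to 5.4% too wide. The power forgone is about 0.5 to 3 points for 7-point differences and under half a point for 10 points.

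The size rests on an assumed center variance. If center is not prognostic after the other covariates, there is no effect. Stronger conclusions are not supported: the error runs toward conservatism, so type I error is not inflated; calculated power without center stays at or above the stated 80% and 95%; and the primary GEE is unaffected. Chapter 5, on randomization logistics, was not in the text examined, so the statement about stratification rests on Chapters 21 to 23.

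**What to change.** In Section 23.3.2.2, state that every 18-month ANCOVA includes baseline TQ and Clinical Center as fixed dummies, whatever the observed balance. Define center as the center of randomization, also for participants who later move under the transfer procedure in Section 14.8.6. State that the 18-month GEE includes center too. In the same edit it would help to list the remaining covariates in advance and to say whether ANCOVA or GEE is the reference method at 18 months.

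The cost is a few lines of SAP text and five of about 200 residual degrees of freedom. No new data, visits or participants are needed.
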